8.3 Follow up visits (Visits 4, 5 and 6)

Follow up visits will be conducted at 4 weeks (1-month FU) (except site #3), 12 weeks (3M FU) and 24 weeks (6M FU) following last treatment.

The 1 month (except site #3), **3 months and 6 months follow up visits** will include the following assessments:

- Standardized medical photography
- 3D Photography

| | | |
|--------------------------------------------------------------------------------------------------------|------------------------------------------------------------------------|-----------------------|
|  I N M O D E | Treatment with the Evoke System for Facial and Submental Laxity | |
| | Protocol No: DO609886A SIRB ID: | Rev. Date: 29 Oct. 20 |

- Urine Pregnancy Test (only last 6 months FU visit)
- Investigator assessment of the skin appearance improvement comparing pre and post treatment using 4-point Likert scale
- Subject’s Improvement and Satisfaction questionnaires
- Post final treatment biopsy will be performed (up to 5 subjects)
- AE evaluation recording
- Concomitant medication recording

9. Adverse Events Reporting

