6.1 Efficacy Endpoints

1. Improvement in in skin laxity comparing pre and at 1 month (except site #3), 3 months and 6 months post last treatment photographs (as assessed by blinded investigators):
 - Success is defined by correct identification of the pre and post treatment photos of patients completed the treatment at 1 month (except site #3), 3 months and 6 months post treatment.
 - At least 2 out of 3 blinded evaluators should agree on the assessment.
2. 3D Photographic analysis will be conducted at 1 month (except site #3), 3 months and 6 months follow up visits and compared to the baseline.
3. Investigator assessment of the skin appearance improvement comparing pre and post treatment using 0 - 4 -points Likert scale at 3 months and 6 months follow up visits:
 - 4 = Significantly marked improvement; 3 = Marked improvement; 2 = Moderate improvement; 1 = Slight improvement; 0 = No difference
4. Improvement assessment will be performed independently by the subject himself 4 points Likert scale questionnaire (Global Aesthetic Improvement Scale), as follows:
 - 4 = Significantly marked improvement; 3 = Marked improvement; 2 = Moderate improvement; 1 = Slight improvement; 0 = No difference.
5. Subject assessment of satisfaction will be filled out by subjects using a 5-points Likert scale, as follows:
 - +2 = Very satisfied; +1 = Satisfied; 0 = Indifferent; -1 = Disappointed; -2 = Very disappointed.
6. Optional: Positive changes in histologic evaluation: up to 5 subjects will undergo biopsies of the treated area for histology at baseline and at 3M follow-up visit. Histological sections will be stained using elastin, H&E and other collagen specific stains.

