7.4 Inclusion Criteria

- Signed informed consent to participate in the study.
- Female and male subjects, ≥ 35 and ≤ 75 years of age at the time of enrolment

| | | |
|---------------------------------------------------------------------------------|------------------------------------------------------------------------|-----------------------|
|  | Treatment with the Evoke System for Facial and Submental Laxity | |
| | Protocol No: DO609886A SIRB ID: | Rev. Date: 29 Oct. 20 |

- If female, not pregnant, lactating and must be either post-menopausal, surgically sterilized, or using a medically acceptable form of birth control at least 3 months prior to enrolment (i.e., oral contraceptives, contraceptive implant, barrier methods with spermicide or abstinence).
- In addition, negative urine pregnancy test as tested before each treatment and at the last visit for women with childbearing potential (e.g. not menopause).
- General good health confirmed by medical history and skin examination of the treated area.
- Willing to have photographs and images taken of the treated areas to be used de-identified in evaluations, publications and presentations.
- The patients should be willing to comply with the study procedure and schedule, including the follow up visit, and will refrain from using any other aesthetic treatment methods for the last 6 months and during the entire study period.

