8.1 Screening and Baseline (Visit 1)

Screening visit will be performed in order to determine subject eligibility and to collect all required demographic and baseline clinical information. Study procedures and available treatment options, including the RF technology will be described in detail to the subject. Subject will be assured that the decision regarding participation in the study is strictly voluntary and that they are free to change their mind at any stage.

The subject will review the informed consent form and the study will be explained to the subject including all risks, potential benefits, procedures, visit requirements, and other alternative treatment options. If the subject qualifies and wishes to participate, he/she will complete the ICF with a signature and date. The original will be retained with subject's records and a copy will be provided to the subject. Subjects will then be screened for study eligibility according to inclusion and exclusion criteria.

The following Demographic and Baseline Measurements will be performed:

- Demographic data including gender, age, race, skin type (Fitzpatrick scale).
- ICF - Prior to any study procedures, informed consent will be obtained. When the subject fully understands the possible benefits and risks of the study, the subject will be asked to sign and date the informed consent form (ICF). The subject will be given a copy of the signed ICF.
- Subject ID - subjects will be assigned a study subject ID number.
- Medical History - A medical history will be obtained to determine if the subject meets the study criteria, including a list of all prescribed and over the counter medications taken within the previous 6 months will be recorded.
- Pregnancy Screen - Subjects who are capable of becoming pregnant will undergo a urine pregnancy test. This will be repeated prior to all treatments, and at the end of the study (last FU visit, 6-month FU).
- If the Screening and Treatment procedures are not conducted on the same day, the urine pregnancy test will be repeated on the first treatment day.
- Photography – Baseline photographs will be obtained using a consistent camera and subject placement settings with a digital imaging system.
- 3D Photography – Baseline 3D pictures will be obtained using 3D system. PI will ensure the same camera is used throughout the study.
- Up to 5 study participants be selected for baseline biopsy

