14.1 Analysis Sets

- Safety Analysis Set

The safety analysis set will include all subjects using Embrace procedures at least a single time.

- Performance Analysis Set

Performance analysis set will consist of all subjects providing at least one post treatment performance measurement.

- Treatment of Missing Values

Only observed data will be used; i.e. missing data will not be imputed.

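### Subjects biopsied in the photographed skin stay in the blinded pre/post photo endpoint, so a biopsy mark can help evaluators pick the later photo (small, cheap to remove)

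*Combined protocol and SAP*

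**What the plan says.** **Endpoint.** Section 6.1 item 1 states: "Success is defined by correct identification of the pre and post treatment photos of patients completed the treatment", at 1 month (not at site #3), 3 months and 6 months. It adds: "At least 2 out of 3 blinded evaluators should agree on the assessment". Section 5 lists this photo comparison as the first primary objective.

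**Biopsies.** Section 6.1 item 6, marked optional, states: "up to 5 subjects will undergo biopsies of the treated area for histology at baseline and at 3M follow-up visit". The synopsis excludes site #3. Section 8.1 has "Up to 5 study participants be selected for baseline biopsy", listed after baseline photography. Section 8.3 lists "Post final treatment biopsy will be performed (up to 5 subjects") after the follow-up photography. Neither section fixes the order within a visit.

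**Photographs.** Section 7.4 requires subjects to be "Willing to have photographs and images taken of the treated areas to be used de-identified in evaluations, publications and presentations". Section 8.2 gives the treatment area as the face and under the chin. Section 8.1 standardises the pictures: "Baseline photographs will be obtained using a consistent camera and subject placement settings with a digital imaging system".

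**Who is analysed.** Section 14.1: "Performance analysis set will consist of all subjects providing at least one post treatment performance measurement". Section 7.2 calls only those who do not complete treatment non-evaluable. Having had a biopsy is not a ground for exclusion.

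**The concern.** Item 1 does not grade improvement. It asks whether an evaluator can tell which photo is later, so anything that dates a photo is scored as efficacy. A biopsy mark in the photographed skin is such a cue. Blinding does not remove it, because it is in the image.

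With photographs first, the baseline photo is unmarked. The 1-, 3- and 6-month photos all follow the baseline biopsy, and the 6-month photo also follows the 3-month biopsy. The study is open label and describes no comparison group, so there is no control rate that would reveal the same cue. At stake is a modest upward shift in a primary success rate that has nothing to do with laxity.

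**Working it through.** The plan gives no success threshold, null rate or sample-size calculation for this endpoint, so there is no stated figure to reproduce. The calculation below only sizes the effect.

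**Inputs from the protocol**
- About 15 subjects per site and five sites (synopsis, 7.1): 5 × 15 = 75 pairs at 3 and 6 months.
- Site #3 has no 1-month visit: 4 × 15 = 60 pairs at 1 month.
- At most 5 biopsied subjects (6.1 item 6), read as a study-wide limit.
- Success needs 2 of 3 evaluators (6.1 item 1).
- Two-sided 0.05 level (14.2).

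**Assumptions**
- Evaluators judge independently, each correct with probability p. Guessing is p = 0.5.
- Photographs precede biopsies.
- Visibility of the mark is unknown, so it is varied.

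**Step 1: success per pair.** S(p) = 3p²(1 − p) + p³.
- S(0.5) = 0.500
- S(0.625) = 0.684 (mark noticed a quarter of the time, otherwise guessing: 0.25 + 0.75 × 0.5 = 0.625)
- S(0.7) = 0.784
- S(0.75) = 0.844 (mark noticed half the time: 0.5 + 0.5 × 0.5 = 0.75)
- S(0.8) = 0.896
- Mark always seen: S(1) = 1

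**Step 2: rise in the success rate.** Rise = 5 × (S with mark − S without mark) / n.

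| Evaluators without the mark | Mark noticed | Rise, n = 75 (3M, 6M) | Rise, n = 60 (1M) |
|---|---|---|---|
| Guess (0.5) | always | 5 × 0.500 / 75 = 3.3 points | 5 × 0.500 / 60 = 4.2 points |
| Guess (0.5) | half the time | 5 × 0.344 / 75 = 2.3 | 5 × 0.344 / 60 = 2.9 |
| Guess (0.5) | a quarter of the time | 5 × 0.184 / 75 = 1.2 | 5 × 0.184 / 60 = 1.5 |
| Right 70% of the time | always | 5 × 0.216 / 75 = 1.4 | 5 × 0.216 / 60 = 1.8 |
| Right 80% of the time | always | 5 × 0.104 / 75 = 0.7 | 5 × 0.104 / 60 = 0.9 |
| Any | no biopsy, or no visible mark | 0 | 0 |

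**Step 3: effect on an error rate, for illustration.** Section 14.2 names only paired t-tests, so an exact two-sided 0.05 binomial test against 50% is assumed, at 75 pairs. It rejects at 47 or more, or at 28 or fewer.
- No marks: upper tail P(Bin(75, 0.5) ≥ 47) = 0.0185, or 1.9%. Both tails: 2 × 0.0185 = 3.7%.
- Five certain successes: upper tail P(Bin(70, 0.5) ≥ 42) = 0.0598, or 6.0%. Lower tail P(Bin(70, 0.5) ≤ 23) = 0.0028. Both tails: 6.3%.
- Each evaluator notices the mark half the time: upper tail 4.3%.

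**Step 4: precision lost by leaving out five pairs.** 95% half-width at a 50% rate = 1.96 × √(0.25 / n).
- 3 and 6 months: n = 75 gives 11.3 points; n = 70 gives 11.7.
- 1 month: n = 60 gives 12.7 points; n = 55 gives 13.2.

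**The case against.** **Visibility is unknown.** The protocol gives no biopsy type, size or exact site. Some views may not show the under-chin area. Three treatments two weeks apart span 4 weeks, so the follow-up photos fall at least about 8, 16 and 28 weeks after a baseline biopsy, and marks may have faded. Biopsies are optional and may not be done. All of this stands: the documents support saying that a mark can reveal the later photo, not that it will.

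**The effect is small.** Even the maximum of 3.3 points is under a third of the 11.3-point half-width. No test is planned for this endpoint, so no planned decision is shown to change. This also stands, and it sets the severity.

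**The order may be settled elsewhere.** The schedule in Appendix 1.0 is not in the text available here and may fix the order within visits. That could settle the direction of the cue, but photographing first would not remove it, because the later photos still follow the baseline biopsy.

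A reader might infer two stronger claims that the documents do not support:
- *The bias can only favour success.* This follows only if photographs come first, which is the listed but not the stated order. If the biopsy came before the baseline photo, that photo could show a fresh wound. Section 9.2 lists crust, blister, burn, bruising and scarring as possible device effects, so a blinded evaluator could take the wounded picture for the post photo and be scored as wrong.
- *The limit is five per site.* Twenty affected pairs at the four eligible sites would make the problem much larger. The protocol says per site for enrolment and replacement (synopsis, 7.1, 7.2) but not for biopsies, so the study-wide reading is the natural one.

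**Conclusion.** The point holds as a minor, cheaply corrected weakness. As written, the plan keeps up to five subjects in a primary endpoint that rewards dating the photos, although biopsies from the same treated skin may date them.

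With photographs before biopsies and a study-wide limit of five, the rise is at most 3.3 points at 3 and 6 months and 4.2 points at 1 month. Reaching that maximum takes five biopsies, marks that are always seen, and evaluators who otherwise guess. Under the assumed exact test at 75 pairs, the upper-tail error would go from 1.9% to at most 6.0%. The upper tail is the one that matters for a false claim of success; over both tails the change is from 3.7% to 6.3%.

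Confidence is high on what the text says and does not say, and low on how visible any mark would be.

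**What to change.** 1. In 6.1 item 1 and 14.1, exclude biopsied subjects from the blinded photo identification and keep them for histology, safety and the other endpoints. Alternatively, keep them and mask the same region in both photos of each of these subjects before blinded review.
2. In 8.1 and 8.3, state that photographs are taken before any biopsy at the same visit. This removes the fresh-wound case at baseline but does not replace step 1.
3. In 6.1 item 6, say that the limit of five is study-wide, if that is what is meant.

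**Cost.** Exclusion loses at most five pairs from one endpoint, and the half-width grows by about half a point or less at each visit (step 4 of the working). Masking loses no pairs and needs only minor image preparation. If enrolment is already under way, reporting item 1 with and without the biopsied subjects is a workable fallback.

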9.1 Definitions

Adverse Event:

An adverse event (AE) is any adverse change in health or side effect that occurs in a study participant during their participation in the study.

Serious Adverse Event (SAE):

A serious adverse event (SAE) is any adverse event that:

- Led to death
- Led to a serious deterioration in the health of the subject that resulted in a life-threatening illness or injury
- Resulted in a permanent impairment of a body structure or a body function
- Required in-subject hospitalization or prolongation of existing hospitalization
- Resulted in medical or surgical intervention to prevent permanent impairment to body structure or a body function
- Led to fatal distress, a congenital abnormality, birth defect or death

Unanticipated Adverse Event:

An unanticipated adverse event is any serious, device-related adverse event, if that event was not previously identified in the risk analysis and Informed Consent form in nature, severity, or frequency.

AE Severity:

Adverse events are graded according to severity as follows (Table 3):

| | |
|----------|-------------------------------------------------------------------------------------------------------------------------|
| Mild | Sign or symptom, usually transient, requiring no special treatment and generally not interfering with usual activities. |
| Moderate | Sign or symptom, which may be ameliorated by simple therapeutic measures; yet, may interfere with usual activity. |

| | | |
|--------------------------------------------------------------------------------------------------------|------------------------------------------------------------------------|-----------------------|
|  I N M O D E | Treatment with the Evoke System for Facial and Submental Laxity | |
| | Protocol No: DO609886A SIRB ID: | Rev. Date: 29 Oct. 20 |

| | |
|--------|-----------------------------------------------------------------------------------------------------------------------------------------------|
| Severe | Sign or symptom that are intense or debilitating and that interfere with usual activities. Recovery is usually aided by therapeutic measures. |
|--------|-----------------------------------------------------------------------------------------------------------------------------------------------|

Relationship to Device:

The relationship of the adverse event to the treatments or procedures is defined as follows (Table 4):

| | |
|------------------------|-----------------------------------------------------------------------------------------------------------------------------------------------------------------------------------------------------------|
| Most Probably Related: | Follows a reasonable temporal sequence from study device delivery/retrieval and cannot be reasonably explained by known characteristics of the subject's clinical data or the surgical procedure applied. |
| Possibly Related: | Follows a reasonable temporal sequence from study device delivery/retrieval but could have been produced by the subject's clinical state or by the surgical procedures regardless of the study device. |
| Probably not Related: | Temporal association is such that the study device is not likely to have had any reasonable association with the observed event. |
| Unrelated | No relationship to study device activation is perceived |

9.2 Anticipated Adverse Events in this Clinical Evaluation

Possible Evoke adverse effects include but are not limited by:

- discomfort or pain,
- excessive skin redness (erythema)
- swelling (edema),
- damage to natural skin texture (crust, blister and burn),
- change of pigmentation (hyper- and hypo-pigmentation),
- bruising,
- scarring.

9.3 Precautions to Minimize Complications

A list of warning and precautions is provided in the Operator Manual which is provided to site personnel. Additionally, the exclusion criteria listed in this protocol further reduce the abovementioned risks.

9.4 Investigator Records

The Investigator will report all Adverse Events which occur with each subject throughout the study and follow-up period and will record them in the CRF Adverse Events Investigation Form. The Investigator will categorize Adverse Events according to:

- Serious or non-serious
- Severity

| | | |
|--------------------------------------------------------------------------------------------------------|------------------------------------------------------------------------|-----------------------|
|  I N M O D E | Treatment with the Evoke System for Facial and Submental Laxity | |
| | Protocol No: DO609886A SIRB ID: | Rev. Date: 29 Oct. 20 |

- Anticipated or unanticipated
- Relationship to device use

9.5 Investigator Reporting of AEs

The Investigator will report all serious adverse events (SAEs) to InMode Ltd by telephone as soon as becoming aware of them. A written follow-up report will be emailed or faxed to InMode Ltd and the reviewing IRB within 24 hours and will include the following information:

1. Nature of AE
2. Statement regarding the degree to which it is considered device related, and rationale.
3. Results of any diagnostic tests that were performed.
4. Description of any treatment implemented.
5. Statement of subject's current clinical status.
6. Investigator's signature and date.

Non-serious adverse events that are unanticipated and may be device related will be reported to the InMode Ltd by telephone within 24 hours. A written follow-up written report will be emailed or faxed to InMode Ltd within 5 working days and will include the following information:

1. Nature of adverse effect.
2. Statement as to why it is considered unanticipated.
3. Statement as to the degree to which it is considered device related, and rationale.
4. Results of any diagnostic tests that were performed.
5. Description of any treatment implemented.
6. Statement of subject's current clinical status.
7. Investigator's signature and date.

All other Adverse Events will be reported in writing to InMode Ltd in writing within 5 working days of the Investigator becoming aware of them.

The Investigator will continue to clinically monitor the AE, with laboratory tests where appropriate, until it is resolved, stabilized or there is a return to baseline.

10. Regulatory Aspects

10.1 Institutional Review Board

The study protocol, informed Consent forms (all versions), and any specific advertising will be submitted to and approved by Sterling Institutional Review Board (IRB), at [name], Toll-Free: [contact], [contact], [contact] before the start of the study. The notification of approval will be provided to the sponsor and site.

10.2 Informed Consent

An Informed Consent that includes all the relevant elements currently required by FDA or state regulations will be provided to each prospective study patient at screening and before enrolling into the study. The type and method of study, any potential or possible hazards, and the patient's right to

| | | |
|---------------------------------------------------------------------------------|------------------------------------------------------------------------|-----------------------|
|  | Treatment with the Evoke System for Facial and Submental Laxity | |
| | Protocol No: DO609886A SIRB ID: | Rev. Date: 29 Oct. 20 |

withdraw from the study at any time will be explained to the patients by the Investigator or designee. Once the Investigator is assured that an individual candidate understands the implications of participating in this study, the patient will be asked to give Consent by signing and dating in the appropriate areas of the Informed Consent form. The Investigator or Designee will also sign and date the form in accordance with ICH E6R2 guidance. A copy of the IRB approved ICF will also be provided to the subject.

10.3 Protocol and Informed Consent Changes

Changes to the protocol or Informed Consent Form will be implemented as amendments to the original document and approved by the IRB. The approvals will be processed in accordance with the established IRB procedures. Any addenda, amendment or revision that substantially alters the study design or increases potential risk to the patient requires the patient's Consent to continue in the study.

10.4 Product Supply and Maintenance

The device will be maintained by the Sponsor, as needed. The device will be used according to the instructions of the Sponsor and manufacturer, InMode. At the end of this study, any materials provided specifically for use in this study may be returned to the Sponsor, as described in the Clinical Trial Agreement and study budget.

